3.3 Recipient exclusion criteria

- History of severe transfusion reaction to plasma products
- Need for oxygen supplementation
- Positive test for COVID-19 antibodies
- Chemotherapy-induced neutropenia ($ANC < 0.5 \times 10^3/\text{mcL}$)
- Immunosuppression medications except for prednisone or steroid equivalent ≤ 10 mg daily.
- Performance status < 50
- Pneumonia by radiographic evaluation

4. Investigational Plan

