4.1 Overall study design

- This is a phase II randomized study of convalescent plasma for the treatment of non-immune individuals with COVID-19 infection at high risk of complications.

- Subjects will be considered as having completed the study after 2 months (+/- 5) days, unless consent withdrawal or death occurs first.
- Subjects will be randomized to receiving convalescent plasma or best supportive care.
- Patients randomized to best supportive care may receive plasma should they require hospitalization for progression of COVID-19 disease.
- Statistical analysis will be performed as described in the statistical section 8.
- The final analysis will be conducted once the last subject completes the 2-month visit or withdraws from the study.

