5.2 Patient procedures and evaluation (see Appendix B)

Patients may be screened, enrolled and randomized remotely. The day of randomization will be designated as day 0 for both Treatment and Control groups. Patients randomized to the treatment arm will need to be seen on the day of infusion which should occur within 48 hours of randomization and be within 96 hours of symptom onset.

5.2.1 Day 0. May be done remotely.

- Screening
- Informed consent must be obtained before performing study related activities (can be from healthcare proxy if subject unable to provide consent due to medical status)
- Baseline Evaluation (at screening)
 1. Demographics (age, sex ethnicity, race)
 2. Medical history
 - a. Date of onset of COVID-19 symptoms
 - b. Date of positive test
 - c. Acute and chronic medical conditions described in the eligibility criteria 3.2.
 - d. Charlson Co-morbidity Index calculation
 3. COVID-19 symptom screen (Y/N)
 - a. Fever (T Max)
 - b. Cough
 - c. Shortness of breath
 - d. Ageusia and/or anosmia
 - e. Myalgias
 - f. Headache
 - g. Other symptoms that the patient attributes to their COVID-19 infection
 4. Documentation of positive nasopharyngeal COVID-19 testing.
 5. Determination of eligibility as per inclusion/exclusion criteria
 6. Randomization

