5.2.2 Plasma infusion day

Patients randomized to the treatment arm will need to be seen on the day of infusion which should occur within 48 hours of randomization and be within 96 hours of symptom onset.

Study plasma administration will be allowed for the Control arm after hospital admission if requested by the patient's medical team.

- On the day of infusion, blood will be drawn for:
 1. Inflammatory markers

- a. D-Dimers
 - b. Ferritin
 - c. CRP
- 2. Serological testing: anti-SARS CoV-2 titers
- 3. Exploratory blood test for genomics (optional)
- 4. Exploratory blood test for cytokines/chemokines (optional)
- 5. Rectal swab for gut microbiome analyses, to be sent to the CDI if possible
- 6. CBC
- 7. Complete chemistry
- 8. ABO Rh

- Procedure:
 - 1. A single unit of approximately 400-500 mL of liquid fresh plasma or 2 units of fresh frozen plasma for a total of approximately 400 mL will be transfused at an approximate rate of 50 mL per hour x 30 minutes, then the rate may be increased up to 150 mL per hour until completion. If plasma availability does not allow for 2 units of FFP, a single unit may be administered.
 - 2. If possible, 10mL of plasma will be collected for research from the infusion line and sent to the CDI
 - 3. The infusion may be slowed or stopped as per investigator's decision for minor transfusion reactions only. The transfusion will be discontinued for any transfusion reactions other than minor allergic reactions.
 - 4. An investigation will be initiated when there are signs of a systemic transfusion reaction.
 - 5. Premedication 30 – 60 minutes prior to the infusion will include 100 mg hydrocortisone IV and may include acetaminophen 650 mg PO and diphenhydramine 25 mg IV. Diphenhydramine 25 mg IV and hydrocortisone 100 mg IV may be repeated as needed for an infusion reaction at the discretion of the investigator.
 - 6. Vitals signs should be monitored following Hackensack Meridian Health Blood and Blood Product Administration SOP guidelines:
 - a. Temperature, pulse, respirations, and blood pressure pre-infusion (within 30 minutes), 15 minutes after the start, every hour during, if a transfusion reaction is suspected or if there is any change in patient condition, post transfusion (5-15 minutes post)

5.2.3 Post enrollment day +3 and day +7 (or closest working day). May be done remotely.

- COVID-19 symptom screen by telephone (Y/N)
 - 1. Fever (T max)
 - 2. Cough
 - 3. Shortness of breath
 - 4. Ageusia and/or anosmia

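### Antibody and neutrophil exclusions have no listed Day 0 test; the first check follows randomization in Treatment only, and no analysis set keeps such patients in

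*Combined protocol and SAP*

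**What the plan says.** Section 3.3 lists among the patient exclusions "Positive test for COVID-19 antibodies", "Chemotherapy-induced neutropenia" (ANC below 0.5), "Need for oxygen supplementation" and "Pneumonia by radiographic evaluation". It does not say when or how each is to be established.

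Section 5.2 states: "Patients may be screened, enrolled and randomized remotely". The Day 0 list in 5.2.1 covers demographics, medical history, the Charlson score, a yes/no symptom screen and documentation of the positive swab. It then gives "Determination of eligibility as per inclusion/exclusion criteria" as item 5 and randomization as item 6. No serology, blood count, vital signs, oximetry or imaging is listed.

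Section 5.2.2 requires Treatment patients to be seen for infusion within 48 hours of randomization. That day's list includes "Serological testing: anti-SARS CoV-2 titers", a CBC and pre-infusion vital signs. Sections 2.2 and 8.3.3 confirm that the pre-infusion titer is for the Treatment group. Control has telephone-type contacts at days +3 and +7 (5.2.3). Its first listed serology is at 2 weeks, if possible (5.2.4).

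Section 4.1 describes the trial as "treatment of non-immune individuals with COVID-19 infection at high risk of complications". Section 8.3.1 counts hospitalization from the start of therapy and compares the arms by the Mantel-Haenszel test. Section 8 defines no analysis population.

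**The concern.** Treatment patients pass a checkpoint after allocation is known, and Control patients do not. A positive titer or a low neutrophil count can come to light there in a Treatment patient, while the equivalent Control patient is never examined. If such Treatment patients are dropped, or are not counted because they were never infused, the arms are no longer the groups that were randomized.

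The direction of the bias depends on who is removed. Removing patients at above-average admission risk favours plasma and inflates the type I error. Removing patients who already have antibodies, if they are at low risk, works against plasma and costs power.

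A smaller consequence concerns the description of the population. Non-immune status is not established for Control, because Control has no baseline serology in the listed schedule.

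**Working it through.** **1. Where each check falls in the body text**

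| Item | Day 0, both arms (5.2.1) | Infusion day, Treatment (5.2.2) | First listed in Control |
|---|---|---|---|
| Serology | not listed | listed | 2 weeks, if possible (5.2.4) |
| CBC (source of an ANC) | not listed | listed | none listed* |
| Vital signs | not listed | listed | none listed* |
| Oximetry, imaging | not listed | not listed | none listed |
| In-person contact | may be remote | required | 2 weeks, preferred |

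*A Control patient who is admitted may receive plasma under 5.2.2 procedures (5.2.5), but only after the primary event.

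The 2-week visit (+/- 3 days) comes after the 10-day window in 8.3.1 and inside the 21-day window in 8.1. On neither window is it a baseline test.

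**2. What happens to a patient found ineligible after randomization.** Section 5.3.1 lists two mandatory reasons for withdrawal from study treatment: toxicity and termination of the study. Post-randomization ineligibility is not covered there or in section 8. With the start of therapy as origin, a Treatment patient who is not infused has no date from which to count.

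**3. The plan's own design, reproduced.** Inputs from 8.1 and 8.2: 8% versus 18%; looks at 51, 102 and 153 per arm; rejection bounds -2.849, -2.015 and -1.645; futility bounds 0.179, -0.944 and -1.645. Simulating binomial trials with a pooled two-proportion Z and futility stops followed gives type I error 0.050 at 18% versus 18%, and power 0.81 at 8% versus 18%. This agrees with the stated 0.05 and at least 0.80.

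**4. Removal from Treatment only, with no plasma effect.** Let f be the fraction removed and r their admission risk. Both are assumptions. The remaining Treatment rate is (0.18 - f·r)/(1 - f), compared with 18% in Control.

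| f | r | Treatment rate | Type I error |
|---|---|---|---|
| 1% | 36% | (0.18 - 0.0036)/0.99 = 17.8% | 0.054 |
| 1% | 50% | (0.18 - 0.005)/0.99 = 17.7% | 0.058 |
| 3% | 36% | (0.18 - 0.0108)/0.97 = 17.4% | 0.064 |
| 3% | 50% | (0.18 - 0.015)/0.97 = 17.0% | 0.077 |
| 1%, 2%, 3% | 100% (extreme) | 17.2%, 16.3%, 15.5% | 0.071, 0.101, 0.141 |
| 10% | 5% (low risk) | (0.18 - 0.005)/0.90 = 19.4% | 0.026 |

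In the last case power is 0.73 if the relative effect of 8/18 holds in eligible patients. If r = 18% there is no bias.

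**5. Power if every randomized patient is kept.** Let s be the seropositive fraction and RR their admission risk relative to seronegative patients, with no plasma effect in them. The seronegative Control rate is p = 0.18/(1 - s + s·RR). The Treatment rate is (1 - s)·p·8/18 + s·RR·p.

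- s = 5%, RR = 0.5: p = 18.5%, Treatment 8.3%, power 0.78.
- s = 10%, RR = 1: p = 18.0%, Treatment 9.0%, power 0.72.
- s = 15%, RR = 2: p = 15.7%, Treatment 10.6%, power 0.55.

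**The case against.** The strongest reply is that the documents contain no one-arm exclusion rule. Eligibility is determined before randomization. The titers have their own purpose as a secondary endpoint. No passage makes infusion-day results an eligibility re-check, and 5.3.2 lets a patient who withdraws consent for treatment continue in follow-up. The exclusions can also be read as known findings, judged from history and records, and oxygen need can be asked about remotely. Appendix B, which holds the recipient schedule, is not reproduced and may list baseline tests. All of this stands, and it makes the point a risk left open rather than an error in a written rule. It does not close the gap, because the body text leaves the choice of analysis set unmade.

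A reader might go further and infer that pneumonia or oxygen need found at the infusion visit would be treated as ineligibility in Treatment, while the same deterioration becomes a primary event in Control. The documents do not support this as a planned mechanism. Section 5.2.2 lists no oximetry or imaging, and no visit lists imaging, so radiographic pneumonia cannot come from any listed procedure. Oxygen need could be noticed when the patient is seen, but nothing says how it would be handled.

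A reader might also take 0.141 as the expected type I error. That figure requires 3% of Treatment patients to be removed and every one of them to have been destined for admission. Nor can the 87% with titers in section 1.4 supply a seropositive fraction: those were hospitalized patients, mostly in their second week, not patients within 96 hours of onset.

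**Conclusion.** The point holds as a gap in the body text, with moderate confidence. Antibody status and ANC are exclusions with no listed pre-randomization test. The first listed check comes after randomization in Treatment only, and neither the analysis set nor the time origin protects the comparison.

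If 1–3% of Treatment patients at 36–50% admission risk were dropped, one-sided type I error would rise from 0.050 to 0.054–0.077. The range 0.071–0.141 is an extreme bound. Dropping low-risk seropositive patients lowers the type I error and costs power, so the direction is not known in advance. These sizes rest on assumed fractions and risks. They do not call the sample size of 306 into question, since it agrees with its stated inputs.

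**What to change.** 1. In 3.3 and 5.2.1, state that every exclusion is judged only on information dated before randomization, in both arms; for example, *known positive antibody test before randomization*.
2. In 8.3.1, analyse every randomized patient in the assigned arm at the final test and both interim looks. Count hospitalization from randomization (day 0) in both arms; without this change of origin, an uninfused Treatment patient cannot be counted. Count an admission arising at the infusion visit as an event, and state that infusion-day results do not remove a patient from the analysis.
3. In 4.1, describe the population as *not known to be antibody-positive* instead of non-immune.

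These are wording changes with no new test or visit, and the clinical decision to infuse is untouched. They should be in place before the first look at 102 patients, because an analysis set chosen after seeing data cannot be defended.

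The cost is power, and it may not be slight. Compared with screening such patients out before randomization, power falls from about 0.81 to between 0.78 and 0.55 on the assumptions in step 5 (0.72 at 10% seropositive and equal risk). Testing both arms before randomization would avoid that loss and support the non-immune description, but it adds tests to a screening step that may be remote.

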4.1 Overall study design

- This is a phase II randomized study of convalescent plasma for the treatment of non-immune individuals with COVID-19 infection at high risk of complications.

- Subjects will be considered as having completed the study after 2 months (+/- 5) days, unless consent withdrawal or death occurs first.
- Subjects will be randomized to receiving convalescent plasma or best supportive care.
- Patients randomized to best supportive care may receive plasma should they require hospitalization for progression of COVID-19 disease.
- Statistical analysis will be performed as described in the statistical section 8.
- The final analysis will be conducted once the last subject completes the 2-month visit or withdraws from the study.

4.2 Overall study duration

- The study begins when the first subject (donor or recipient) signs the informed consent. The study will end once the last enrolled subject completes the study (likely a recipient).
- The expected duration of the study is approximately 12 months.

5. Treatment Plan

5.1 Donor procedures and evaluation

All activities pertaining to donor recruitment, enrollment, collection, product handling and processing will take place at Hackensack University Medical Center (HUMC) and John Theurer Cancer Center at HUMC. This facility is FDA-registered and AABB accredited, attesting to robust quality oversight of all operations. All donor-related procedures pertaining to this study are detailed in our SOP 800 01 “COVID-19 Convalescent Plasma Procurement” in Appendix A.

Donors may alternatively be enrolled and collected under IND 19824, as all procedures of evaluation, collection and product handling are identical.

As donor eligibility defined by the FDA may change, donors may be eligible if they follow updated eligibility as per FDA guidelines: <https://www.fda.gov/vaccines-blood-biologics/investigational-new-drug-ind-or-device-exemption-ide-process-cber/recommendations-investigational-covid-19-convalescent-plasma>

5.1.1 Donor recruitment and screening (see Appendix A)

- Mechanism for recruitment will include advertising in the local community where recent outbreaks have occurred.
- Individuals who agree to participate will do so under full informed consent.
- Individuals who agree to participate will undergo pre-donation screening by a clinical health care provider (visit 1).
- Only those individuals who satisfy all criteria for collection as determined through medical evaluation and laboratory testing described in Appendix A will proceed to a second visit (visit 2) during which the collection will take place. Visit 2 will occur within seven days of visit 1.

1. Visit 1:

- a. History and targeted physical examination if collecting at JTCC
- b. Donor health questionnaire
- c. Nasopharyngeal swab for COVID-19
- d. Blood for SARS-CoV-2 neutralizing antibody
- e. Blood tests as described in SOP 800.01 section “Donor Evaluation and Eligibility” subsection L (Appendix A), for collections at the JTCC

2. Visit 2:

- a. Donor health questionnaire
- b. Blood tests as described in SOP 800.01 section “Donor Evaluation and Eligibility” subsection L (Appendix A)
- c. Apheresis procedure as described in section 5.1.2 and Appendix A if collecting at the JTCC.

5.1.2 Donor plasma collection (see Appendix A)

- The plasma collection will be performed by apheresis at the John Theurer Cancer Center (JTCC) Collection Facility at HUMC as per “COVID-19 Convalescent Plasma Procurement” SOP (Appendix A) or the donor will be referred to an outside licensed Blood Center for plasmapheresis.
- The JTCC houses a FACT accredited Collection Facility, NJ Blood Bank license 10317, FDA (BMT FEI) Registration 3004726780.
- The plasma collection will be performed using either the Trima Accel® System by Terumo BCT (Appendix A SOP 800 01).
- As per routine practice, samples will be collected at the time of donation for testing for transfusion-transmissible infections (all donors), ABO and red cell antibodies (all donors) and HLA antibodies (female donors), in accordance with FDA regulation 21 CFR 610.40, and the donation must be found suitable (21 CFR 630.30).
- Target collection volume: 400-500mL in a single collection bag or two collection bags of 200mL. The Trima Accel® system considers the total blood volume and will make recommendations to the volume that can be removed safely. Therefore, the collection goal will be either 400mL or the machine recommended maximum volume, whichever is smallest.
- Labeling will be in accordance with FDA regulations 21CFR 606.121.
- The plasma will be maintained in quarantine pending laboratory test results (i.e. infectious screening, ABO and RhD status, Red cell and HLA antibodies).
- If laboratory testing is acceptable (i.e. negative infectious and antibody screening), the products will be appropriately labeled and distributed to hospital blood bank for storage.
- In the event of an abnormal test result, the product will be discarded, and the donor will be notified by the blood center as is standard practice.
- Donors may donate plasma every \geq 7 days. The donor screening procedure described in section 5.1.1 “visit 2” will need to be repeated for each subsequent donation on the day of plasmapheresis, with the addition of blood for SARS-CoV-2 neutralizing antibody

5.1.3 Product handling

Product handling including labeling, testing, transportation, distribution and record keeping including chain of custody recording will be performed in accordance with regulations and HUMC SOP 800.01 “COVID-19 Convalescent Plasma Procurement” (Appendix A).

5.2 Patient procedures and evaluation (see Appendix B)

Patients may be screened, enrolled and randomized remotely. The day of randomization will be designated as day 0 for both Treatment and Control groups. Patients randomized to the treatment arm will need to be seen on the day of infusion which should occur within 48 hours of randomization and be within 96 hours of symptom onset.

5.2.1 Day 0. May be done remotely.

- Screening
- Informed consent must be obtained before performing study related activities (can be from healthcare proxy if subject unable to provide consent due to medical status)
- Baseline Evaluation (at screening)
 1. Demographics (age, sex ethnicity, race)
 2. Medical history
 - a. Date of onset of COVID-19 symptoms
 - b. Date of positive test
 - c. Acute and chronic medical conditions described in the eligibility criteria 3.2.
 - d. Charlson Co-morbidity Index calculation
 3. COVID-19 symptom screen (Y/N)
 - a. Fever (T Max)
 - b. Cough
 - c. Shortness of breath
 - d. Ageusia and/or anosmia
 - e. Myalgias
 - f. Headache
 - g. Other symptoms that the patient attributes to their COVID-19 infection
 4. Documentation of positive nasopharyngeal COVID-19 testing.
 5. Determination of eligibility as per inclusion/exclusion criteria
 6. Randomization

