8.1 Hypothesis

The primary objective is the hospitalization rate of patients with early COVID-19 infection at high-risk of admission. Suppose the hospitalization rate by 21 days from therapy initiation is 8% for the Treatment group (P_t) and 18% for the Control group (P_c). This phase II design will aim at the following hypothesis:

The design has a type I error rate at 0.05 with statistical power at least 0.80.

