8.2 Study design

This trial will follow a one-sided three-stage O'Brien-Fleming design as follows.²³

The first stage analysis will be after 51 subjects in each arm, that is after a total of 102 subjects. If the Z statistic is greater than or equal to 0.179 (p-value ≥ 0.571), the hypothesis H_0 is accepted and the trial stops, we conclude the Treatment is not worth pursuing; if the Z statistic is less than or equal to -2.849 (p-value ≤ 0.002), the hypothesis H_0 is rejected and early evidence for promising efficacy is established. Otherwise, the trial continues to the next stage.

The second stage analysis will be after 102 subjects in each arm, that is after a total of 204 subjects. If the Z statistic is greater than or equal to -0.944 (p-value ≥ 0.173), the hypothesis H_0 is accepted and the trial stops, we conclude the Treatment is not worth pursuing; and if the Z statistic is less than or equal to -2.015 (p-value ≤ 0.022), the hypothesis H_0 is rejected and early evidence for promising efficacy is established. Otherwise, the trial continues to the final stage.

At the final stage, a total of 306 subjects will be recruit and 153 of them for each arm. The hypothesis H_0 is rejected for efficacy if the Z statistic is less than -1.64504 (p-value < 0.4498). Otherwise, the H_0 is not rejected.

Stage	Cumulative total sample size N	Cumulative sample size for treatment group N(Grp 1)	Cumulative sample size for control group N(Grp 2)	Evidence for undesired rate if Z statistic \geq (Accept H_0 if Z-statistic \geq)	Evidence for desired rate if Z statistic \leq (Reject H_0 if Z-statistic \leq)	Evidence for undesired rate if p-value \geq (Accept H_0 if p-value \geq)	Evidence for desired rate if p-value \leq (Reject H_0 if p-value \leq)
1	102	51	51	0.17929	-2.84929	0.57115	0.00219
2	204	102	102	-0.94399	-2.01475	0.17259	0.02197
3	306	153	153	-1.64504	-1.64504	0.04998	0.04998

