8.3. Analysis Plan

8.3.1 Primary Endpoints

The primary endpoint of the phase II study is the hospitalization rate at 10 days from therapy initiation of patients with early COVID-19 infection at high-risk of admission. The hospitalization rate will be summarized by frequency (%) and compared between the Treatment and Control arms by Mantel-Haenszel test. There will be two interim analyses. Analysis reports will be provided to the DSMB to decide if there is a pronounced treatment effect or futility. A detailed interim analysis plan will be provided before the start of the interim analysis.

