8.4 Charlson Co-morbidity Index22

Patients will be stratified in 4 groups based on their Charlson Co-morbidity Index scoring:

Low score ≤ 3 points; moderate score = 4, 5 points; high score = 6, 7 points; very high score ≥ 8 points.

One Point for each:

- Myocardial infarction (history, not ECG changes only)
- Congestive heart failure
- Peripheral disease (includes aortic aneurysm ≥ 6 cm)
- Cerebrovascular disease: CVA with mild or no residua or TIA
- Dementia
- Chronic pulmonary disease
- Connective tissue disease
- Peptic ulcer disease
- Mild liver disease (without portal hypertension, includes chronic hepatitis)
- Diabetes without end-organ damage (excludes diet-controlled alone)

Two Points for each:

- Hemiplegia
- Moderate or severe renal disease
- Diabetes with end-organ damage (retinopathy, neuropathy, nephropathy, or brittle diabetes)
- Tumor without metastasis (exclude if ≥ 5 y from diagnosis)
- Leukemia (acute or chronic)
- Lymphoma

Three Points for each:

- Moderate or severe liver disease

Six Points for each:

- Metastatic solid tumor
- AIDS (not just HIV positive)

<https://www.mdcalc.com/charlson-comorbidity-index-cci>

9. Regulatory consideration

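### The primary comparison names no covariate; pre-specifying adjustment for age would be worth about 0 to 3 points of power at little cost

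*Combined protocol and SAP*

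**What the plan says.** - **Primary test.** Section 8.3.1: "The hospitalization rate will be summarized by frequency (%) and compared between the Treatment and Control arms by Mantel-Haenszel test". No strata and no covariates are named. The only regression model planned for hospitalization, in section 8.3.3, concerns donor parameters.
- **Baseline data.** Section 5.2.1 collects age among the demographics on day 0, before randomization and in both arms. For timing it lists "Date of onset of COVID-19 symptoms", a calendar date.
- **Age as a risk factor.** Section 3.2 requires patients to be at least 30 and puts age 65 or over first among the high-risk features. Symptom onset must lie within 96 hours.
- **Stratification.** Section 8.4: "Patients will be stratified in 4 groups based on their Charlson Co-morbidity Index scoring". The items listed there give no points for age.
- **Design.** Section 8.2: "This trial will follow a one-sided three-stage" design; "The first stage analysis will be after 51 subjects in each arm", and at the end "a total of 306 subjects will be recruit and 153 of them for each arm". Section 8.1: the assumed rate "is 8% for the Treatment group (P_t) and 18% for the Control group (P_c"), and "The design has a type I error rate at 0.05 with statistical power at least 0.80".

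**The concern.** Age is a baseline value that the protocol itself treats as predicting admission. It is already collected, and neither the randomization nor the primary test uses it. A 40-year-old whose only risk feature is a BMI of 30 and an 85-year-old whose only other feature is hypertension both score zero on the listed Charlson items and fall in the same low stratum.

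If age does predict admission, an unadjusted test leaves explainable variation in the error term. A chance age imbalance then moves the observed difference, most of all at the first look with 51 patients per arm. Power has almost no reserve over the 0.80 target, so a small gain in precision is worth having. A covariate agreed in advance also avoids a post hoc dispute should the arms differ in age.

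**Working it through.** **1. Reproduce the stated design.** Inputs from sections 8.1 and 8.2: rates 0.08 and 0.18; 51, 102 and 153 per arm (information 1/3, 2/3, 1); efficacy bounds -2.84929, -2.01475, -1.64504; futility bounds 0.17929, -0.94399, -1.64504.

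Expected Z at the end, unpooled variance:

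(0.08 - 0.18) / sqrt[(0.08 x 0.92 + 0.18 x 0.82) / 153] = -0.10 / sqrt(0.2212 / 153) = -2.63

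Numerical integration over the three looks gives:
- type I error 0.0500 (futility binding);
- power 80.2% unpooled and 79.4% pooled; a 400,000-trial binomial simulation gives 80.6%;
- 153 per arm as the smallest size that reaches 80% with unpooled variance.

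The plan's figures reproduce without any adjustment.

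**2. Expected events at each look**, from n per arm x (0.08 + 0.18): 51 x 0.26 = 13.3; 102 x 0.26 = 26.5; 153 x 0.26 = 39.8.

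**3. What adjustment buys for a given prognostic strength.** If the covariates explain a share R2 of the variance, the standard error is multiplied by sqrt(1 - R2), and 306 patients give the precision of 306 / (1 - R2) unadjusted patients. Put the other way, 306 x (1 - R2) adjusted patients match 306 unadjusted.

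| R2 (assumed) | SE ratio | Power at 306 (unpooled) | 306 x (1 - R2) |
|---|---|---|---|
| 0 | 1.000 | 80.2% | 306 |
| 0.02 | 0.990 | 80.9% | 300 |
| 0.05 | 0.975 | 81.9% | 291 |
| 0.07 | 0.964 | 82.6% | 285 |
| 0.09 | 0.954 | 83.3% | 278 |

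**4. What R2 might be.** The documents give no figure, so this is a range under assumptions: age mean 60, SD 12, from 30 years; onset uniform over 0 to 96 hours; logistic risk with marginal rates held at 8% and 18%. With q1 and q0 the individual risks under Treatment and Control,

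R2 = 1 - {2 E[q1(1 - q1)] + 2 E[q0(1 - q0)] + Var(q1 - q0)} / {2 x 0.2212}

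- Age alone, odds ratio per 10 years of 1.2, 1.5 and 2.0: 0.5%, 2.5% and 6.9%.
- Onset alone, odds ratio per 24 hours of 0.9, 1.3 and 0.7: 0.2%, 1.0% and 1.8%.
- Both together: at most 8.6%.

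Read against the table, that is about 0 to 3 points of power, or at most about 306 - 278 = 28 patients' worth of precision. Most of it comes from age.

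**5. Do the section 8.2 bounds carry over?** Two separate simulations ran all three looks with those bounds and Charlson-stratified blocks. The gain is measured against the unadjusted test, so it includes anything that comes from the Charlson terms.

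| Model | Age odds ratio per 10 years | Power, unadjusted | Power, adjusted |
|---|---|---|---|
| Charlson + age | 1.0 | 0.812 | 0.810 |
| Charlson + age | 1.4 | 0.811 | 0.820 |
| Charlson + age | 1.8 | 0.815 | 0.834 |
| Charlson + age + onset | none (no prognostic effects) | 0.800 | 0.798 |
| Charlson + age + onset | 1.4 | 0.805 | 0.812 |
| Charlson + age + onset | 1.8 | 0.816 | 0.842 |

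Type I error of the adjusted score test was 0.047 to 0.051 for Charlson plus age. For the three-term model it was 0.051 to 0.054 at an 18% null rate and 0.046 to 0.056 at 10%. In the second simulation, Charlson plus age without onset gave 0.813 and 0.839, so onset time added almost nothing.

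**The case against.** **The present test is adequate.** The design meets its own targets unadjusted, and randomization already allows for chance imbalance. This stands, and it is why the point concerns efficiency only.

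**The gain is assumed.** No document states how strongly age predicts admission, and the lower end of the range is zero. This also stands. The answer is that almost nothing is lost if age proves uninformative (0.812 against 0.810).

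**The first look is too sparse.** Three Charlson terms, age and an intercept are five parameters on about 13 expected events. Under assumed splits of the Charlson groups from 70/20/7/3% to 40/30/20/10%, at least one non-empty group has no events at that look in 33 to 79% of trials if risk is flat across groups, and in 14 to 46% if it rises. The maximum-likelihood coefficient for such a group is then not finite. This does not defeat the score test, which fits only the model without arm. A group with no events gets fitted risk zero and contributes nothing to the score or its variance. The simulated type I error agrees. What stands is that adjustment is not wholly free and needs a written fallback.

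**Stratification may already cover age.** Section 8.4 links an external calculator, and whether the score actually used counts age cannot be settled from the documents. The listed items do not count it. If the score does, the gain is smaller.

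**Stronger readings that a reader might infer.**
- *Time since onset belongs in the model.* Section 1.1 argues that timing changes how well antibody works. That is modification of the treatment effect and not prediction of admission, and a main-effect term does not address it. The range is limited to 96 hours, and a date does not supply hours.
- *Power would be well above 80%.* One final test at Z of -1.645 or below gives 0.842, but the three-stage bounds give 0.806. Gains must be counted from the latter.

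**Conclusion.** The concern holds as an efficiency improvement. The primary test names no covariate, although age is available at baseline in both arms, is a risk feature by the protocol's own account, and is absent from the listed Charlson items. Adjustment for Charlson group and continuous age is worth about 0 to 3 points over the three-stage design's roughly 80%, with type I error near 0.05 under the existing bounds.

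The size rests on assumed age distributions and odds ratios. It also rests on the 8% and 18% rates, which section 8.1 states for 21 days while section 8.3.1 sets the endpoint at 10 days. A reader might infer that the unadjusted analysis is biased, or that a known amount of precision is being thrown away. The documents support neither: the test is valid, and they give no prognostic strength from which a loss could be established.

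**What to change.** Amend section 8.3.1 before the first look and carry the same definition into the interim analysis plan promised there:

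1. Name the four Charlson randomization groups as strata. This comes first, since the section does not say whether the Mantel-Haenszel test uses them.
2. Define the primary Z at every look as the score test for arm from a logistic model with Charlson group and continuous age: Z = U / sqrt(V), where U sums (outcome - fitted risk) over the Treatment arm, the fitted risk comes from the model without arm, and V is the matching efficient variance. Negative values favour Treatment, as in section 8.2. Keep the section 8.2 bounds.
3. Report the standardized risk difference, and give the Charlson-stratified Mantel-Haenszel test as the sensitivity analysis.
4. State a fallback for sparse groups, for example merging adjacent Charlson groups in a fixed order if the model does not converge.
5. Leave out hours since onset. If timing is wanted, use days from onset to randomization as an optional term.
6. State in section 8.4 whether the score used for randomization counts age.

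The cost is plan wording and a little programming. No new data are needed. The downside is a model with few events at the first look.
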